## 1 List of Abbreviations

Abbreviation	Abbreviation definition
UVR	Ultraviolet Radiation
UVB	Ultraviolet B Radiation
25(OH)D	25-hydroxyvitamin D
SPS	Solius Photobiologic System
MED	Minimal Erythema Dose

## 2 Protocol Summary

Title:	Evaluating the effect of Solius Photobiological System in improving serum levels of 25-hydroxyvitamin D in vitamin D deficient/insufficient adults: A feasibility study
Population:	Healthy adults ages 22 years and older; both sexes, approximately 14 adults for serum 25-hydroxyvitamin D screening, 10 adults with vitamin D deficiency/insufficiency for the feasibility study
Intervention:	The study treatment is a weekly exposure to the Solius Photobiological System, which emits Ultraviolet B Radiation (UVB). This will be accomplished with an established dose of UVB radiation for 4 weeks. SOLIUS delivers 0.6 Minimal Erythema Dose (MED) to achieve non-perceivable erythema for a therapeutic dose.
Objectives:	To assess the safety and effectiveness of the Solius Photobiological System in improving serum levels of 25-hydroxyvitamin D in vitamin D deficient/insufficient adults of various skin types
Design/Methodology:	We will conduct an interventional study to determine the changes in serum 25-hydroxyvitamin D levels in subjects who received Ultraviolet B Radiation (UVB) generated by the Solius Photobiological System for 4 weeks. Subjects will first undergo an evaluation of each individual's sensitivity to the Solius Photobiological System UVB using the device titration system for the first 5 weeks. Once determined after the 5 weeks, the subjects will be enrolled in a 4-week study where they will be exposed to their individualized titration evaluation. Approximately 14 adult subjects will be enrolled for serum 25-hydroxyvitamin D screening. We expect to enroll 10 vitamin D-deficient or insufficient subjects in this study. Serum 25-hydroxyvitamin D levels will be measured prior to the first titration (week 2), prior to the intervention (week 6) and after end of the study, and the changes in serum 25-hydroxyvitamin D levels will be analyzed. We expect that the levels will increase from the baseline.
Total Study Duration:	6 months

---

**Subject Participation Duration:** 10 weeks including one week for screening, 5 weeks for titration, 4 weeks for intervention

---

### 3 Background/Rationale & Purpose

#### 3.1 Background Information

Vitamin D deficiency has been a worldwide health problem for over a century, now affecting over 1 billion people on this planet. Although technology is drastically advancing, we still are unable to put an end to this health emergency.

Vitamin D can be introduced in the body in two ways, 1) via diet and 2) through the sun. Few foods naturally contain vitamin D (either D2 or D3) such as oily fish. For instance fresh, wild salmon (3.5oz or 100g) has between 600-1000 IU of vitamin D3. Canned tuna (3.6oz or 102 g) has about 230 IU of vitamin D3. Sun-dried mushrooms and egg yolks are also viable sources of vitamin D. Sun-dried shiitake mushrooms have about 1600 IU of vitamin D2 whereas egg yolks have about 20 IU of vitamin D2 or vitamin D3. There are some fortified foods that also contain vitamin D; fortified milk and fortified orange juice each has about 100 IU/8 oz of vitamin D3. Some cereals, such as Quaker Oatmeal has as much as 40 IU vitamin D/cup. Margarine has about 60 IU of vitamin D/tablespoon. In a study that looked at the plasma levels of 25(OH)D3 amongst fish eaters and non-fish eaters (vegans and vegetarians), those who did not consume fish had lower levels of 25(OH)D3 in both the summer months (20%) and winter months (38%). Thus the consumption of fish in the diet is critical in maintaining vitamin D status throughout the year, especially during the winter months.

When assessing the optimal dietary intake of vitamin D, there might be some controversy as to which guideline to follow. The Institute of Medicine (IOM) issued guidelines to maintain adequate serum 25(OH)D levels above 20 ng/mL. The Endocrine Society's guidelines reflect the needs to treat and prevent vitamin D deficiency and maintain a 25(OH)D status above 30 ng/mL. One would have to consume a significant amount of fish and fortified food products to meet the above recommendations. Thus it is critical that we incorporate sun exposure into our everyday lives, and/or take vitamin D supplements.

When ultraviolet B (UVB) radiation (wavelength of 290-320 nm) from the sun is absorbed into the skin, it converts 7-DHC, which is predominantly located in the stratum spinosum and stratum basale, to previtamin D3, which is thermodynamically unstable. Over several hours it isomerizes into vitamin D3. The vitamin D3 from the skin and the vitamin D2 from food and supplements enters the circulation and are hydroxylated in the liver by a 25-hydroxylase to become 25-hydroxyvitaminD (25(OH)D), which is the major circulating form of vitamin D. 25(OH)D is hydroxylated again in the kidneys by 1alpha-hydroxylase to become 1,25-dihydroxyvitamin D (1,25(OH)2D), which is the active form of vitamin D. When calcium levels are too high, 24-hydroxylase activity increases, hydroxylating C24 and making, 24,25-Dihydroxyvitamin D (24,25(OH)2D) and 1,24,25-trihydroxyvitamin D (1,24,25-(OH)3D). This step begins the process of the degradation of both metabolites into inactive water soluble metabolites that

can be excreted in the bile. The ability to maintain 25(OH)D levels via sun exposure is influenced by the zenith angle of the sun. The zenith angle is defined as the oblique angle between the sun's rays and the earth's surface. The time of day, season, and latitude on the earth's surface all affect the zenith angle. Above 37° latitude during the months of November through February, there is a significant decrease in the amount of UVB photons hitting the earth's surface, as much as 80%-100% depending on latitude. Thus, for those living in areas at a zenith angle incompatible for producing vitamin D in the winter, they need to obtain their vitamin D via supplements and/or food containing or fortified with vitamin D.

Those living above 37° latitude during the months of November through February could also rely on artificial UVB light sources such as the Sperti lamp or UVB emitting LEDs. These lights permit the skin to convert 7-dehydrocholesterol into vitamin D allowing the body to maintain adequate vitamin D levels while avoiding exposure to the sun. In particular, these lights are resourceful to those having fat malabsorption disorders such as Crohn's disease, cystic fibrosis, and/or gastric bypass. For these individuals who are unable to absorb vitamin D from the diet, exposure to UVB is the primary way of maintaining an adequate vitamin D status.

UVB phototherapy is a potential solution to the problem. Importantly, narrowband UVB (NB-UVB) phototherapy can be safely used. Long-term studies to date do not indicate a significantly increased risk of skin cancer in an age- and sex-matched control population who have not received UVB phototherapy. In a 2005 literature review, a search from 1966 to June 2002 was conducted. Eleven studies involving about 3400 subjects (including those with >300 lifetime treatments) were included. Except for 1 Finnish study, all studies showed no increased skin cancer risk with UVB phototherapy. In a 2012 systematic literature review examining NB-UVB and risk of skin cancer, four studies followed a total of 6,385 subjects. None of the four studies found an increased risk of skin cancer in psoriasis subjects treated with NBUVB. The above studies were mostly in Caucasians with skin types I-III. In a 2011 study of 445 Koreans (skin type III-V) treated with NB-UVB, no melanoma cases were reported within the mean follow-up period of 34.4 months. The investigators also concluded that there were no statistically significant differences in non-melanoma skin cancer between the NB-UVB and control groups. In the largest study on the safety of vitiligo treatment ever conducted, a 2020 retrospective cohort enrolled 60,321 subjects with vitiligo. Subjects were classified into 5 groups: 0 sessions of NB-UVB; 1-49 sessions; 50-99 sessions; 100-199 sessions; and ≥200 sessions. 717 subjects had at least 500 phototherapy sessions. The risk of nonmelanoma skin cancer did not increase with increasing total sessions of NB-UVB. Further, the subjects who had at least 500 sessions of NB-UVB phototherapy had no greater risk of skin cancer than the subjects who did not undergo NB-UVB phototherapy at all.

Solius has created The Solius Photobiologic System (SPS), which is an experiential device that allows a user to receive a calibrated and calculated dose of vitamin D using wavelengths of UV light that facilitate the body's endogenous production of vitamin D and a variety of biologically controlled feedback mechanisms. The output of SPS is very similar to a NB-UVB device, but without the wavelengths that are less effective in endogenous vitamin D production. Exposure of individuals with varying skin types to these lights will enable us to observe the effect of artificial UVR exposure in creating vitamin D in individuals with varying shades of skin color. The benefit of this lamp will allow individuals who live in northern locations or individuals with malabsorption problems to create vitamin D.

Solius previously has completed two human clinical trials. The first study was a pilot feasibility study aimed to validate if the Solius Photobiological System efficiently stimulated the endogenous vitamin D process. The second study was a randomized non-inferiority study comparing the SOLIUS device to oral vitamin D supplements.

In a prospective cohort study (QR-TRP-002), six healthy adults with Fitzpatrick skin types I, II, and III were exposed to a 0.75 minimal erythema dose (MED) of UVB radiation to approximately 75% of their body surface area once per week for 4 weeks. The individual dose was determined with Fitzpatrick skin typing, followed by exposure of the underneath of one forearm to 10 successively increasing durations of exposure to UVB. The subjects had a significant increase in mean 25(OH)D from  $22.8 \pm 13.9$  ng/ml to  $27.2 \pm 12.0$  ng/ml ( $P<0.05$ ), representing a 19% increase over baseline after 4 weekly UVB exposures. No adverse events occurred.

Another study was performed on military personnel. Military personnel are at high risk for low vitamin D status which is common in individuals who regularly perform extreme physical exertion, particularly in combination with periods of psychological stress, inadequate nutrition, and sleep disruption. A total of 98 participants enrolled in the study; 10 (10.2%) either dropped out or were removed after enrollment. The final sample included 45 participants in the supplement and 43 in the phototherapy group. There were no between group differences noted based on age or gender distribution ( $P=0.06$ ). There were also no between group differences observed with respect to race / ethnicity, Fitzpatrick skin type, birth location with respect to 37th parallel, prior diagnoses of vitamin D deficiency, vitamin D supplementation history, stress fractures, or family history of bone disorders, and total number of hours per week of sun exposure, with  $P > 0.05$  for these groups.

The median serum 25(OH)D levels at baseline for the supplement and phototherapy were 25.0 ng/mL (IQR 21.0–32.0) and 28.0 ng/mL (IQR 22.0–35.0), respectively. By month three, the phototherapy group showed significantly higher levels of serum 25(OH)D than the supplement group ( $P=0.01$ ,  $\eta^2=0.08$ ) with a median level of 25.5 ng/mL (IQR 21.0–29.8) compared to a median level of 30.0 ng/mL (IQR 25.8–37.0) for the phototherapy group. By the four-month follow up the two groups again showed a slight difference in serum 25(OH)D levels with higher levels in the phototherapy group ( $P=0.04$ ,  $\eta^2=0.05$ ). At this timepoint the supplement group had decreased from baseline to median levels of 21.0 ng/mL (IQR 17.0–30.0) and phototherapy returned to baseline (median 27.0 ng/mL, IQR 22.0–32.5) (supplementary documents).

With suboptimal intake of key nutrients like calcium and vitamin D, historically low compliance with taking pills, and low sun exposure, limited potential to optimize serum 25(OH)D continues to pose a threat to physical and mental health, disease prevention, and resilience so critical to individual wellness and readiness. At a time when self-care measures are highly valued for health promotion, programmed UVB photobiologic therapy, available as a kiosk in the community, appears to be a safe, efficacious alternative to oral vitamin D supplementation.

As discussed above, there is an ever growing need to improve the vitamin D status of the global population. Many individuals who live above 37° latitude and/or have malabsorption problems will greatly benefit from an artificial light source to combat their increased risk for vitamin D deficiency. The purpose of this study is to observe the effects of exposure of individuals of varying shades of skin color

to Solius light source. The findings from the study have enormous health implications as it could be a potential treatment plan for many people battling vitamin D deficiency.

This study will be conducted in compliance with the protocol, applicable regulatory requirements, and BMC/BU Medical Campus Human Research Protection policies and procedures.

### **3.2 Rationale and Purpose**

We aim to conduct this feasibility study in anticipation of conducting a more extensive study that will be used to evaluate the safety and efficacy of the Solius Photobiologic system for improvement of vitamin D status.

## **4 Objectives**

### **4.1 Study endpoint**

The endpoints are to gain experience in using this device to determine if exposure to UVB generated by the Solius Photobiologic system will lead to some improvement in vitamin D status.

#### **Study Outcome Measures**

Improvement of serum levels of 25(OH)D will be measured by 25(OH)D analysis at baseline, prior to the intervention (week 6) and the end of the study. Serum 25(OH)D levels measurement will be performed by Quest Diagnostics.

#### **4.1.1 Endpoint Measures**

1. At each visit, the subjects will be asked to report any adverse events and any skin changes. These adverse events will be tabulated and reported at the study completion.
2. Blood samples will be obtained from all subjects at baseline (prior to the first titration, week 2), prior to the intervention (week 6) and end of the study. Blood samples will be sent to the Quest Diagnostics or to the Boston Medical Center's clinical laboratory for determining the serum 25(OH)D levels.

## 5 Study Design

This is a pilot interventional study aiming to gain experience in using of the Solius Photobiologic System that is designed to increase the serum levels of 25(OH)D in a vitamin D deficient/insufficient adult population. We will make our best effort to recruit individuals with different Fitzpatrick skin types. The study will be conducted at Boston University after it is approved by Boston University's Institutional Review Board. The use of a single location will keep uniform natural UVB exposure of the study as opposed to multiple geographic locations what would create a wide variety of natural exposures to UVB and result in a less uniform impact of this natural exposure in both study arm.

Table 1. The below guidelines will be used to make this distinction:

Table 1: Fitzpatrick Skin Types		
Skin type	Typical Features	Tanning ability
I	Pale white skin, blue/green eyes, blond/red hair	Always burns, does not tan
II	Fair skin, blue eyes	Burns easily, tans poorly
III	Darker white skin	Tans after initial burn
IV	Light brown skin	Burns minimally, tans easily
V	Brown skin	Rarely burns, tans darkly easily
VI	Dark brown or black skin	Never burns, always tans darkly

Each subject will be categorized into one of 6 Fitzpatrick skin types, type I, II III, IV and skin type V or VI. Skin types V and VI will be combined to represent the group with the darkest skin tone for subgroup analysis.

A total of 14 adult subjects with 5 skin types groups (I, II, III, IV and V/ VI) will be enrolled for vitamin D deficiency/ insufficiency screening. The screening test for 25(OH)D will be performed by the Boston

Medical Center's clinical laboratory which is able to perform the test within 24 hours. We expect at least 80% of the population in the Boston area has a level of 25(OH)D below 30 ng/ml. Thus, we expect to enroll approximately 14 subjects with different group skin types to enroll 10 vitamin D deficient or insufficient subjects in this study to receive UV exposure by the Solius Photobiologic System. The device will have a strip of colored LED installed inside the light towers. Both UV lamps and purple LED will turn on during the treatment.

Blood samples will be obtained prior to the first titration (week 2) , prior to the intervention (week 6) and end of the study. The blood samples will be sent to Quest Diagnostics or the Boston Medical Center's clinical laboratory for determining the serum 25(OH)D levels. The study design is summarized in Table 2.

**Table 2. Outcomes measurement at each time point of the study for both study groups**

Activity	Baseline Wk 1	Titration					Intervention			
		Wk 2	Wk 3	Wk 4	Wk 5	Wk 6	Wk 7	Wk 8	Wk 9	Wk 10
Informed Consent	X									
Inclusion/Exclusion	X									
Medical History	X									
Demographics/ Skin typing	X									
UVB Exposure		X	X	X	X	X	X	X	X	X
25(OH)D	X	X					X			X
Sun exposure/ Vit. D food checklist	X	X								X
Concomitant Medications	X	X					X	X	X	X
Adverse Events		X					X	X	X	X

## 6 Potential Risks and Benefits

### 6.1 Risks

The main acute adverse effects of narrowband UVB (NB-UVB) are erythema and induction of photosensitivity diseases, such as polymorphic light eruption (PLE). Although the risk of erythema episodes may be increased by concomitant phototoxic drugs, this can be minimized by undertaking a baseline minimal erythema dose (MED) and establishing treatment protocols based on an individual's MED. This also allows any unsuspected abnormal photosensitivity diseases to be detected, in particular solar urticaria or chronic actinic dermatitis (CAD). Induction of PLE may occur during a treatment course but generally can be accommodated via dose adjustments and judicious use of topical corticosteroid, without the need to stop NB-UVB. Other uncommon side-effects, such as psoriatic lesional blistering, occasionally occur but generally treatment is very well-tolerated.

Overexposure to our artificial UVB source may incur similar symptoms to a mild sunburn (slight reddish coloration to the skin). The Solius Photobiological System was designed to minimize total UVB exposure to minimize the potential for sunburn. To make sure subjects do not develop redness (erythema) or psoriatic lesional blistering, the exposure will set for the lamp to 60% or 0.60 of the minimal erythema dose (MED) for each individuals' skin type.

Over exposure to the UVB to the eyes may cause photokeratitis.

To prevent the overexposure, the subject's dosage will be determined during titration period. Eye protection will be provided to the subjects before each treatment. The device software will require subject confirmation that is in place before treatment can be delivered.

As the appropriate doses are individualized to the subject, to establish the correct dose, each subject will complete a titration period of up to 5 weeks. The titration period will start with an erythemally weighted dose of 10.53 mJ/cm^2 to 43.07 mJ/cm^2 (depending on skin type) and increase by 26 – 36%

each step until a maximum erythemally weighted dose of 34.88 mJ/cm^2 – 109.33 mJ/cm^2 (depending on skin type) or the subject shows a skin reaction. This dose will be the subject's dosage.

The subject's dosage will be administered under conditions of full-body exposure (males in swimming trunks or briefs and females in bikini or bra and panties) of 0.6 minimal erythema dose (MED) once per week for 4 weeks. At each visit, the subject will report adverse events and any skin changes.

We will have the blood samples drawn by trained professionals to minimize the risk of hematoma formation, bleeding, or infection at the site of needle insertion. Study staff will update subjects in a timely way on any new information that may affect their health, welfare, or decision to stay in this study. Any and all side effects reported will be recorded in the subjects' file in the study binder. Subjects will be instructed to call the study staff or PI immediately if any side effects do occur. The PI will advise the subjects according to the symptoms reported. After the determination, all samples will be de-identified. The PI will be available to answer any questions or concerns from potential subjects prior to consenting. We have a plan to protect subject privacy and confidentiality, which is explained in the plan to protect subject privacy and confidentiality in the data section.

Vitamin D deficiency and insufficiency is common in adults due to an inadequate dietary intake of vitamin D and or inadequate sun exposure. Chronic vitamin D deficiency and insufficiency can lead to bone loss resulting in increased risk of fracture later in life. Chronic vitamin D deficiency can also cause a mineralization defect of the skeleton resulting in osteomalacia. Short term (10 weeks) vitamin D deficiency and insufficiency is not associated with significant bone loss or osteomalacia. Therefore, the participants are at no increased risk for fracture or osteomalacia. At the termination of this study those participants will be encouraged to take a vitamin D supplement along the guidelines recommended by the Endocrine Society to correct their vitamin D deficiency and insufficiency.

Chronic excessive exposure to sunlight or ultraviolet radiation for prolonged periods of time, in years or decades, can increase risk for nonmelanoma skin cancer. To minimize the risk the subjects will be 22 years and older and will be exposed to suberythemal doses of UVB radiation for the duration of the study

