### 6.3 Analysis of Risks in Relation to Benefits

Highly trained professionals will be performing the blood draws which is likely to be a chance of risk. The adverse skin reaction from the Solius Photobiological System such as skin erythema and pruritus is a possible risk in this study. However, this study will expose the participants to a relatively low intensity of UVB (0.6 MED), so the risk of adverse reaction is minimal. All the participants will be asked for their willingness to receive the intervention at every exposure and will be questioned and examined for any potential adverse reaction due to the intervention. If any significant adverse reaction is detected, the intervention will immediately stop and the affected participant will receive immediate medical attention. Significant adverse reactions include photokeratitis, moderate to severe skin tenderness, itchiness and tightening, skin blistering, or bruising or tearing of skin. The risks of breach of confidentiality are highly unlikely, and therefore benefits will greatly outweigh the risks.

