## 8 Study Intervention

Subjects (n=10) will be exposed to the Solius Photobiological System which includes exposure to visible purple LEDs and invisible UVB radiation. The study intervention will involve an investigational UVB emitting device, The Solius Photobiologic System created by Solius. The Solius Photobiological System emits UVB. To make sure subjects do not develop redness, the exposure will set for the lamp to 60% or 0.60 of the minimal erythema dose (MED) for each individual's skin type.

As the appropriate doses are individualized to the subject, to establish the correct dose, each subject will complete a titration period of up to 5 weeks. The titration period will start with an erythema weighted dose of 10.53 mJ/cm^2 to 43.07 mJ/cm^2 (depending on skin type) and increase by 26 – 36% each step until a maximum erythema weighted dose of 34.88 mJ/cm^2 – 109.33 mJ/cm^2 (depending on skin type) or the subject shows a skin reaction. This dose will be the subject's dosage.

The device will have a strip of purple LEDs installed inside the light towers. Both UV lamps and purple LEDs will turn on during the treatment. According to a previous study by Solius where 43 subjects were exposed to a 0.6 MED, the stimulation of cutaneous vitamin D and subsequent increase in serum concentrations of 25(OH)D from phototherapy was compared to the effect of a Recommended Daily Allowance (RDA) based dose of 600 IU vitamin D3 supplement daily for 10 weeks. Thus, we will expose these individuals a 0.6 MED once per week for 4 weeks to observe the effect on 25(OH)D serum concentration.

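### For a subject whose titration ends in erythema, sections 6.1 and 8 as written make the reacting dose the weekly dosage, against the suberythemal commitment in 6.1 and the withdrawal rule in 10.4

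*Combined protocol and SAP*

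**What the plan says.** The dosage rule stands in section 6.1 and again in section 8. Titration starts at 10.53 to 43.07 mJ/cm², depending on skin type, and rises by 26–36% per step. It ends at a maximum of 34.88 to 109.33 mJ/cm² "or the subject shows a skin reaction. This dose will be the subject's dosage". Section 6.1 gives the purpose: "To prevent the overexposure, the subject's dosage will be determined during titration period". Section 2 carries the result forward, with subjects "enrolled in a 4-week study where they will be exposed to their individualized titration evaluation".

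The treatment dose is also stated as a fraction of the MED:

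- Section 2: "SOLIUS delivers 0.6 Minimal Erythema Dose (MED) to achieve non-perceivable erythema for a therapeutic dose".
- Section 6.1, directly after the dosage rule: the subject's dosage is given at full-body exposure "of 0.6 minimal erythema dose (MED) once per week for 4 weeks".
- Section 8: "To make sure subjects do not develop redness, the exposure will set for the lamp to 60% or 0.60" of the MED. The sentence then ties that MED to the individual's skin type, and 6.1 has a near-identical sentence.
- Section 6.1 on long-term risk: subjects "will be exposed to suberythemal doses of UVB radiation for the duration of the study".
- Section 6.3 on risk and benefit: "this study will expose the participants to a relatively low intensity of UVB (0.6 MED), so the risk of adverse reaction is minimal".

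Two other sections deal with reactions. In 10.2, staff interview the subject before each exposure and decide on continuation by the degree of the reaction. The device software asks about pinkness and may keep the dose, lower it, or block the account. In 10.4, a subject is withdrawn for an adverse reaction to the light, with erythema and pruritus as examples and no grade.

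**The concern.** The dosage sentence follows two ways of ending titration and does not separate them. For a subject who reaches the maximum without reacting, carrying that dose forward makes sense. For a subject who reacts, the same sentence points to the dose that produced the reaction. If the reaction is erythema, that dose is by definition at or above the subject's erythema threshold at that time. Nothing in the documents says to apply 0.6 to it, to step back, or to return to the last tolerated dose. The term skin reaction is not defined.

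The matter is participant safety and dose definition. The subjects affected are those most sensitive to UVB for their skin type. The minimal-risk statement in 6.3 rests on the 0.6 MED dose, and a feasibility study meant to prepare a larger one needs a dosing rule that others can follow.

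**Working it through.** **Inputs.** Start doses, maxima, step sizes and the titration length of up to five weeks are from sections 6.1 and 8; the 0.6 MED is from 2, 6.1, 6.3 and 8. No MED in mJ/cm² is given, so 0.6 MED cannot be reproduced as an absolute dose.

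**1. Is the ladder coherent?** Assume five doses with equal ratios, the lowest start paired with the lowest maximum and the highest with the highest.

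- Low: (34.88/10.53)^(1/4) = 3.312^(1/4) = 1.349, giving 10.53, 14.21, 19.16, 25.85, 34.88 mJ/cm².
- High: (109.33/43.07)^(1/4) = 2.538^(1/4) = 1.262, giving 43.07, 54.36, 68.62, 86.62, 109.33 mJ/cm².

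Both ratios fit the stated 26–36%.

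**2. The reacting dose, if MED means the subject's own.** Let D be the reacting dose and r the step ratio (1.26–1.36). Suppose D/r was tolerated, D gave erythema and the MED is stable. Then D lies between 1 and r MED.

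- D = 1.00 to 1.36 MED.
- D/(0.6 MED) = 1/0.6 to 1.36/0.6 = 1.67 to 2.27.
- One step back, D/r = 1/1.36 to 1 = 0.74 to 1.00 MED, still above 0.6.

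For a reaction at the first step there is no tolerated dose, so no upper limit follows. The subject's MED is then at most 10.53 (low) or 43.07 (high) mJ/cm², and 0.6 MED is at most 0.6 × 10.53 = 6.32 or 0.6 × 43.07 = 25.84 mJ/cm².

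**3. If the MED shifts during the study.** For D to become 0.6 MED, the MED must rise by D/0.6 − 1 = 67–127%. For D to become suberythemal, it must rise by more than D − 1 = 0–36%. A modest shift could therefore remove the suberythemal conflict but not the 0.6 MED conflict on the individual reading.

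**4. If MED means a nominal skin-type value.** A subject more sensitive than is typical for the skin type can redden at 0.6 of the nominal MED. The reacting dose and the stated 0.6 MED could then coincide, and the multiples in step 2 do not apply. The suberythemal and no-redness statements are still contradicted.

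**5. Instructions for one event, erythema during titration.**

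| Section | Instruction read literally |
|---|---|
| 6.1 and 8, dosage sentence | Treat at the reacting dose |
| 2, 6.1 and 8, stated dose | Treat at 0.6 MED |
| 10.2 | Staff decide on continuation; software may keep, lower or block the dose |
| 10.4 | Withdraw |

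These cannot all be followed.

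**6. A candidate reduced dose.** 0.6 × D/r = 0.6/1.36 to 0.6 = 0.44 to 0.60 MED under the assumptions of step 2. In mJ/cm² on the ladders of step 1:

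| Reaction at dose | 2 | 3 | 4 | 5 |
|---|---|---|---|---|
| Low ladder (start 10.53) | 6.32 | 8.52 | 11.50 | 15.51 |
| High ladder (start 43.07) | 25.84 | 32.62 | 41.17 | 51.97 |

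The reduced dose is below the starting dose for a reaction at doses 2–3 (low) or 2–4 (high).

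**The case against.** The strongest reply is that other text keeps a reactor from being treated at the reacting dose. Section 10.4 is mandatory and names erythema. The sentence after the dosage rule in 6.1 says that the dosage is given at 0.6 MED, which can be read as governing what is delivered. Staff must interview the subject and decide on continuation before every exposure, and 6.3 stops the intervention for significant reactions. The device's own dosing rule is not in the documents and may be safer than the text.

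Much of this stands. A reader might infer that the protocol will expose reactors to four weeks at 1.00–1.36 MED. The documents do not support that: 10.4 applied literally would remove such a subject first, and 10.2 may lower or block the dose. But 10.4 does not reconcile the text. It withdraws a subject for an event that 6.1 and 8 use to set the dose, and 6.3 and 10.2 grade reactions where 10.4 does not. The software may also keep the dose, and no reduction rule is given.

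A reader might also infer that the reacting dose can never be 0.6 MED. That holds only if the MED is the subject's own. Section 6.1 supports that reading where it speaks of protocols based on an individual's MED, but 6.1 and 8 also tie the 0.6 to skin type. The text is ambiguous.

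**Conclusion.** The plan gives incompatible instructions for a subject who reddens during titration, and the natural reading of one of them makes the reddening dose the weekly dosage. The conflict with the suberythemal and no-redness statements holds on either meaning of MED, provided the reaction is erythema and the threshold does not rise past the reacting dose. The conflict with 0.6 MED, at 1.67–2.27 times the stated dose, further requires an individual MED, a tolerated previous step and a stable MED. Absolute doses stay within the skin-type maximum throughout.

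Actual overexposure is possible but not shown. The documents give no reaction rate for this titration, so the number affected is unknown. Whether the maximum dose in a non-reactor equals 0.6 MED cannot be determined from the documents. The point does not bear on power. It should be fixed, because the present wording states a wrong rule for the most sensitive subjects and the correction is small.

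**What to change.** In 6.1 and 8, define skin reaction by type and grade, say whether 0.6 MED is individual or by skin type, and replace the dosage sentence with:

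> A subject who reaches the skin-type maximum without a reaction is treated at that maximum. A subject who shows erythema is not treated at the reacting dose; the dosage is reduced below the last tolerated dose (0.6 times the last tolerated dose if 0.6 of the individual MED is intended and the device can deliver it). A subject who reacts at the first step, or for whom the device cannot deliver the reduced dose, is not exposed again without investigator review and a reduced dose, or is withdrawn.

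In 10.4, keep withdrawal for adverse reactions. Except only a mild titration reaction that is judged under 10.2 not to require removal and is followed by that reduction. A wider exception would weaken the strongest protection that reactors now have.

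The essential change is that a reacting dose is never carried forward. The multiplier is one choice among several; 0.6 times the reacting dose, taken as the MED, is another.

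The cost is protocol wording and an IRB amendment, with no added visits or subjects. Early reactors may need a device setting below the starting dose. With the multiplier shown, reactors receive 0–27% less than 0.6 of their own MED (1 − 0.44/0.60 = 27%), and their 25(OH)D rise may be smaller. On the low ladder, a subject who reacts at the fifth dose would receive 15.51 mJ/cm² against 34.88 for a non-reactor.
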